## 5.6 Safety Analysis

All safety analysis will be performed using the safety population.

## 5.6.1 Study Drug Exposure

Extent of treatment exposure will be summarized for seribantumab, fulvestrant, and exemestane as follows:

- Number and percentage of patients beginning 1, 2, 3, ...., 6 and > 6 cycles
- Number of cycles started will be treated as a continuous variable
- Actual Dose received defined as total actual dose (mg) divided by BSA (m^2)

- Relative Actual Dose = [Total actual dose (mg) divided by Total intended dose (mg)] x 100, where total intended dose is defined as the dose as prescribed which is summed from first to last date irrespective of missing, interruption, or reduction.
- Total Exposure (weeks) derived as (last dose date first dose date + 1)
- Dose intensity (mg/m^2/wk) will be summarized as Actual Dose received divided by (duration in days multiplied by 7)

#### Treatment Delays and Dose Modifications

#### Definitions:

A **dose reduction** is defined as actual dose taken is  $\leq 33\%$  than the prescribed dose on any given day for any reason with the exception of a day with total dose administered of 0mg is not considered a dose reduction.

A dose interruptions/delay/missed dose is defined as a planned dosing day with 0 mg administered

Patients will be summarized by frequency and percentage according to:

- Patients with at least one dose reduction overall and by cycle
- Patients with at least one dose reduction due to an adverse event
- Total number of dose reductions per patient
- Number of dose interruptions/missed overall and by cycle

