## 5.3.1. Fulvestrant Formulation, Packaging, Labeling, and Storage

Please refer to the fulvestrant package insert located in the pharmacy binder for specific information on the fulvestrant formulation.

Fulvestrant will be supplied by the Sponsor and labeled for investigational use only according to local regulations. Fulvestrant will be supplied as two 5-mL clear neutral glass barrels, each containing 250 mg/5 mL of fulvestrant solution for intramuscular injection and fitted with a tamper evident closure. The solution for injection is a clear, colorless to yellow, viscous liquid.

Fulvestrant should be stored at refrigerated (2-8 °C). It should be stored protected from light and in the original packaging until the time of use.

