# 5.3.2. Fulvestrant Dosage and Administration

The approved dose of fulvestrant is 500 mg administered intramuscularly into the buttocks. The injection should be as two 5 mL injections and should be administered slowly (1-2 minutes per injection). Injections should be given on days 1 and 15 of Cycle 1, and on day 1 of each subsequent 28 day cycle.

Technique for administration of the injection is outlined in the package insert. Because fulvestrant is administered intramuscularly, it should be used with caution in patients with bleeding diatheses, thrombocytopenia, or anticoagulant use.

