#### 5.4. Rules for Dose Omissions and Modified Treatment Schedules

It is intended that seribantumab and fulvestrant dosing occur on schedule per the protocol. In the event that dosing of any study drug has been held for 28 consecutive days and the investigator does not wish to continue dosing, the patient should be discontinued from treatment.

Dose modifications of seribantumab are not allowed. Any dose modifications to fulvestrant should be performed in line with the local package insert, and should be discussed and approved by the Sponsor prior to implementation.

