#### 5.6.2 Adverse Events

Adverse events will be coded using the latest MedDRA dictionary at the time of coding. NCI CTCAE v4.0 will be used to grade severity. Frequencies and percentages will be reported by System Organ Class (SOC) and preferred term (PT). Patients with multiple events for a category will be counted once in the highest CTCAE classification. Summary tables will include treatment-emergent AEs, unless specified otherwise. Treatment-emergent adverse events (TEAEs) will be defined as patients based on the event onset date relative to first dose of study drug in the study. Missing onset date for an event will be considered as TEAE. Adverse events with a starting date 30 or more days after the last dose date are not considered TEAEs. Relatedness will be considered: Possibly, Probably, or Definitely related per case report form classification. If relatedness is missing the adverse event will be considered TEAE. The order of reporting the events in summary tables will be according to the following where applicable:

- SOC will be alphabetically reported
- Descending order of frequencies according to the number of patients in the seribantumab treatment group experiencing an adverse event
- PT will be alphabetically reported

The following tables will be reported:

- TEAE
  - Any TEAE by SOC
  - Any TEAE by SOC and PT\*
  - Any TEAE by PT
  - Any TEAE by PT by NCI CTCAE Grade
  - Any TEAE by PT by cycle

- Any TEAE by PT by NCI CTCAE Grade by cycle
- Related TEAE
  - Any TEAE by SOC and PT\*
  - Any TEAE by PT
  - Any TEAE by PT by NCI CTCAE Grade
- TEAE NCI CTCAE Grade 3 or higher
  - Any TEAE by SOC and PT
  - Any TEAE by PT
- Related TEAE NCI CTCAE Grade 3 or higher
  - Any TEAE by SOC and PT
  - Any TEAE by PT
- SAE TEAEs only
  - Any SAE by SOC and PT\*
  - Any SAE by PT
- TEAE Various
  - Any TEAE Resulting in Dose Reduction
  - Any TEAE Resulting in Treatment Discontinuation
  - Any TEAE Resulting in Death

In the AE preferred term summary tables, a patient having multiple events within a System Organ Class is counted only once for that SOC. Similarly, a patient having multiple events under a preferred term is counted only once for that PT. Listings will be provided for all adverse event data.

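### The SAP's dose-reduction definition lacks its comparative word, and neither literal reading counts a half dose of fulvestrant or seribantumab

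*SAP*

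**What the plan says.** The definition is in SAP 5.6.1, under Treatment Delays and Dose Modifications. It sets the limit for a reduction at ≤ 33%, and the words that come after that figure are: "than the prescribed dose on any given day for any reason with the exception of a day with total dose administered of 0mg". Days with nothing given form a separate category: an interruption, delay or missed dose "is defined as a planned dosing day with 0 mg administered". The same section then lists the summaries that use the flag: patients with at least one reduction overall and by cycle, patients with at least one due to an adverse event, and the number of reductions per patient. SAP 5.6.2 separately lists a table titled "Any TEAE Resulting in Dose Reduction" and does not say where its data come from.

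On the doses themselves, Protocol 5.3.2 states: "The approved dose of fulvestrant is 500 mg administered intramuscularly into the buttocks". Protocol 5.3.1 describes the supply as two barrels, each "containing 250 mg/5 mL of fulvestrant solution for intramuscular injection". Protocol 5.2.3 gives seribantumab as a fixed 3000 mg. Protocol 5.2.5 and 5.4 do not allow seribantumab dose reductions or modifications. For the other drug, Protocol 5.4 says: "Any dose modifications to fulvestrant should be performed in line with the local package insert", with prior sponsor approval.

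**The concern.** The sentence sets a threshold without saying what the 33% measures. A programmer has to choose between 33% of the prescribed dose and 33% below it, and the two choices classify the same dosing day differently. More importantly, neither choice does what a dose-reduction flag is for, because a substantial partial dose falls outside both.

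Fulvestrant is the drug whose dose the protocol allows to be modified. Partial seribantumab doses could also arise, because Protocol 5.2.4 has infusions stopped for Grade 2 to 4 reactions and bars further treatment after Grade 3 or 4. The definition applies whatever the reason for the shortfall, so it covers both routes. At stake is whether the exposure tables describe how treatment was actually delivered. A table showing few or no reductions could reflect the wording of the rule and not the conduct of the trial.

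**Working it through.** The threshold is a definition, so there is no planned figure to reproduce. The check classifies doses under each reading.

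**Inputs.** Fulvestrant full dose: 2 × 250 mg = 500 mg (Protocol 5.3.1 and 5.3.2). Seribantumab full dose: 3000 mg (Protocol 5.2.3), which agrees with the synopsis volume and concentration, 120 mL × 25 mg/mL = 3000 mg. Threshold: 33%, with 0 mg days excluded (SAP 5.6.1).

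**Rules.**
- Reading A, at most 33% of prescribed: 0 < actual/prescribed ≤ 0.33.
- Reading B, at most 33% below prescribed: actual > 0 and (prescribed − actual)/prescribed ≤ 0.33.
- Rule C, a correction and not a reading of the text: actual > 0 and (prescribed − actual)/prescribed ≥ 0.33.

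**Cut-offs.**
- A: 0.33 × 500 = 165 mg fulvestrant; 0.33 × 3000 = 990 mg seribantumab. Doses up to these values count.
- B: 0.67 × 500 = 335 mg; 0.67 × 3000 = 2010 mg. Doses at or above these values count.
- C: the same 335 mg and 2010 mg, but non-zero doses at or below them count.

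| Dose given | % of prescribed | % below | A | B | C |
|---|---|---|---|---|---|
| Fulvestrant 125 mg | 25 | 75 | yes | no | yes |
| Fulvestrant 165 mg | 33 | 67 | yes | no | yes |
| Fulvestrant 250 mg | 50 | 50 | no | no | yes |
| Fulvestrant 335 mg | 67 | 33 | no | yes | yes |
| Fulvestrant 495 mg | 99 | 1 | no | yes | no |
| Fulvestrant 500 mg | 100 | 0 | no | only if zero shortfall counts | no |
| Seribantumab 990 mg | 33 | 67 | yes | no | yes |
| Seribantumab 1500 mg | 50 | 50 | no | no | yes |
| Seribantumab 2010 mg | 67 | 33 | no | yes | yes |
| Seribantumab 3000 mg | 100 | 0 | no | only if zero shortfall counts | no |

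**Result.** Any dose strictly between 33% and 67% of prescribed is missed under both A and B. That is above 165 mg and below 335 mg for fulvestrant, and above 990 mg and below 2010 mg for seribantumab. Reading B also inverts the concept: a 1% shortfall counts and a 75% shortfall does not.

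**Reference dose.** The text does not say whether the prescribed dose is the planned protocol dose or the dose ordered that day. If a lowered fulvestrant dose of 250 mg had itself been prescribed, then 250/250 = 100% of prescribed. Reading A would miss it, and so would rule C if it kept the same reference.

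**The case against.** **The intent is obvious.** A reader would probably take the sentence to mean at least 33% less than prescribed. That is likely, but it requires both an added word and a reversed inequality, so it is a correction. The sign may have been misread when the PDF was converted, which cannot be excluded. A ≥ sign would still leave the comparison incomplete.

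**Full doses would not really be counted.** A reader might infer from reading B that every full dose becomes a reduction. Arithmetically 0% is at most 33%, but a dose equal to the prescribed dose is not reduced in any ordinary sense. This objection stands. What remains is that trivial shortfalls count and a half dose does not.

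**A 250 mg dose may never occur.** One might infer from the two-barrel supply that half a dose is the most likely fulvestrant modification. The documents do not say so. They refer modifications to the local package insert, list no reduced dose levels and give no expected frequency. The 250 mg dose is an illustration only.

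**Seribantumab partial doses should be few.** Protocol 5.2.4 has Grade 2 infusions resumed once the reaction resolves, and reports past infusion reactions in fewer than 1% of patients, all Grade 1 or 2. This stands as a limit on how often the flag would matter for that drug.

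**The adverse-event table has its own source.** It is tempting to say that all reduction outputs would be wrong. Protocol 9.2 has the investigator record the action taken with study drug for each event, and the table in SAP 5.6.2 could be built from that field. It is affected only if it uses the derived flag, which the SAP leaves open.

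**Under-dosing is still visible elsewhere.** SAP 5.6.1 also reports relative actual dose, with the intended total summed regardless of reductions. As an illustration, one 250 mg dose among four planned 500 mg doses gives 1750/2000 = 87.5%. This softens the consequence, but it does not repair the counts of reductions by patient, by cycle or by cause.

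**Conclusion.** The definition is wrong as written and needs correcting. Neither literal reading counts a dose between 33% and 67% of prescribed, which includes a half dose of either drug, and no other section settles the meaning.

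The consequence is small. It reaches the descriptive dose-reduction summaries in SAP 5.6.1, and possibly one adverse-event table. It does not touch the primary endpoint or its test. How many patients would be misclassified cannot be estimated, because the documents give no expected rate of partial dosing and no list of permitted fulvestrant levels.

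The finding assumes that the inequality sign is as it appears in the text, and that the percentages are taken against the full protocol doses of 500 mg and 3000 mg. The SAP also identifies itself as written for a different protocol number and a phase 3 exemestane or fulvestrant design. That is a separate and larger matter; it does not change this defect, but it offers a natural occasion to correct it.

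**What to change.** Before database lock, restate the sentence with an explicit comparator, direction and reference dose. One form is: a dose reduction is a non-zero administered dose at least 33% below the planned protocol dose, that is, 67% or less of it. Naming the planned protocol dose keeps a dose that was lowered in advance from being compared with itself. The 33% cut-off in this form is inferred from the existing text, so the sponsor should confirm it. It is a label for analysis and has no bearing on how patients are dosed.

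In the same edit:
- report reductions separately for each drug;
- show incomplete infusions separately from reductions;
- state whether the table of adverse events resulting in dose reduction uses this flag or the action-taken field on the case report form.

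The core change is one sentence in the SAP, with short additions for the reporting points and matching edits to table shells and programs. The documents show no need for new data collection.

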#### 5.6.2 Adverse Events

Adverse events will be coded using the latest MedDRA dictionary at the time of coding. NCI CTCAE v4.0 will be used to grade severity. Frequencies and percentages will be reported by System Organ Class (SOC) and preferred term (PT). Patients with multiple events for a category will be counted once in the highest CTCAE classification. Summary tables will include treatment-emergent AEs, unless specified otherwise. Treatment-emergent adverse events (TEAEs) will be defined as patients based on the event onset date relative to first dose of study drug in the study. Missing onset date for an event will be considered as TEAE. Adverse events with a starting date 30 or more days after the last dose date are not considered TEAEs. Relatedness will be considered: Possibly, Probably, or Definitely related per case report form classification. If relatedness is missing the adverse event will be considered TEAE. The order of reporting the events in summary tables will be according to the following where applicable:

- SOC will be alphabetically reported
- Descending order of frequencies according to the number of patients in the seribantumab treatment group experiencing an adverse event
- PT will be alphabetically reported

The following tables will be reported:

- TEAE
  - Any TEAE by SOC
  - Any TEAE by SOC and PT\*
  - Any TEAE by PT
  - Any TEAE by PT by NCI CTCAE Grade
  - Any TEAE by PT by cycle

- Any TEAE by PT by NCI CTCAE Grade by cycle
- Related TEAE
  - Any TEAE by SOC and PT\*
  - Any TEAE by PT
  - Any TEAE by PT by NCI CTCAE Grade
- TEAE NCI CTCAE Grade 3 or higher
  - Any TEAE by SOC and PT
  - Any TEAE by PT
- Related TEAE NCI CTCAE Grade 3 or higher
  - Any TEAE by SOC and PT
  - Any TEAE by PT
- SAE TEAEs only
  - Any SAE by SOC and PT\*
  - Any SAE by PT
- TEAE Various
  - Any TEAE Resulting in Dose Reduction
  - Any TEAE Resulting in Treatment Discontinuation
  - Any TEAE Resulting in Death

In the AE preferred term summary tables, a patient having multiple events within a System Organ Class is counted only once for that SOC. Similarly, a patient having multiple events under a preferred term is counted only once for that PT. Listings will be provided for all adverse event data.

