### Arm B (Comparator Arm):

- Placebo: intravenously (IV) on days 1 and 15 of each 28-day cycle
- Fulvestrant: 500 mg IM on days 1 and 15 of Cycle 1, and on day 1 of each subsequent 28 day cycle

Treatment must start within 7 days following randomization. It is intended that patients will be treated until investigator-assessed disease progression or unacceptable toxicity, whichever comes first. Tumor assessments will be measured and recorded by the local radiologist every 8 weeks (+/- 5 days) from randomization using the RECIST guidelines (version 1.1). Tumor assessments will be performed every 8 weeks regardless of dose delays or dose interruptions, until investigator-assessed progressive disease. Patients who come off study treatment prior to disease progression, for reasons including patient or physician decision or unacceptable toxicity, will continue to undergo tumor assessments every 8 weeks (±5 days) until investigator assessed PD. Patients will be treated according to local assessment of tumor scans, and the primary analysis will be conducted based on investigator assessments.

All patients will have a follow-up visit scheduled 30 days (±7 days) after the last dose of study treatment, regardless of reason for treatment termination. Patients will not be allowed to cross over from placebo to seribantumab.

Survival follow up will be required for all patients every 2 months from the 30-day follow-up visit until death, loss to follow-up, withdrawal of consent, or study termination. After patients discontinue study treatment, subsequent anti-cancer therapies will be collected at the same time as survival follow-up.

An independent data monitoring committee (DMC) will be established to monitor emerging safety data and evaluate for trial efficacy. The DMC will regularly monitor safety data over the course of the study in accordance with the DMC Charter.

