# 10.2. Statistical Hypothesis and Determination of Sample Size

The primary hypothesis is to test for differences in progression-free survival (PFS) distributions.

A stratified log-rank test will be used to analyze PFS differences with the stratification factors in the model: Statistical significance will be determined by using a one-sided type I error of 0.10. A stratified Cox proportional hazards model will be used to estimate the hazard ratio using geographic region (US, non-US) and bone-only disease (yes, no) as stratification factors.

The median PFS for the control arm (fulvestrant + placebo) is assumed to be 4.0 months in this patient population. A total of 58 PFS events will be required across two treatment arms randomized in a 1:1 ratio giving 80% power to detect a hazard ratio (HR)  $\leq$  0.57 (mPFS: 4 v 7), assuming a 1-sided significance level of 0.10. Approximately 200 patients will need to be screened in order to accrue 80 randomized in approximately 16 months with a total study duration of 20 months.

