#### 10.5.4. Safety Analyses

Safety analyses (adverse events and laboratory analyses) will be performed using the safety population. Adverse events will be coded using the latest MedDRA dictionary. Severity of adverse events will be graded according to the NCI CTCAE version 4.03.

Treatment-emergent adverse events (TEAEs) are defined as any event that occurred after the first dose of study drug and was not present prior to study drug administration or worsened in severity after study drug administration. TEAEs will be collected through the end of treatment visit. Frequency and percent summaries will be presented for treatment-emergent adverse events (TEAE) defined as adverse events that occur or worsen in severity following the first dose of seribantumab, or fulvestrant. Additional tabulations include serious adverse events (SAE), TEAE-related to seribantumab, fulvestrant and TEAE grade  $\geq 3$ , and discontinuation due to TEAE. Adverse events will be summarized by System Organ Class and preferred term. All adverse event data will be listed by patient.

Maximum and minimum decrease in continuous laboratory data will be reported. Bar graphs depicting treatment arms will be reported. Frequency and percent of abnormal laboratory values (L/ULN, 2\*L/ULN) will be assessed. Shift to most severe toxicity grade will be summarized.

Vital signs, ECG, and ECHO/MUGA will be tabulated for the change from baseline by time point. Additional analyses may be performed as described in detail within the SAP.

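### Adverse events are summarised only as patient percentages, so events that accrue over time would look more frequent on seribantumab if the assumed PFS gain lengthens treatment

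*SAP*

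**What the plan says.** **Summary measure.** Protocol 10.5.4: "Frequency and percent summaries will be presented for treatment-emergent adverse events (TEAE"). SAP 5.6.2: "Frequencies and percentages will be reported by System Organ Class (SOC) and preferred term (PT"), with each patient counted once per term. The same measure serves the related, grade 3 or higher, serious and discontinuation/death tables. Neither document plans a rate per time at risk or a time-to-first-event analysis for adverse events.

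**Time at risk.** Protocol 3.1: "patients will be treated until investigator-assessed disease progression or unacceptable toxicity, whichever comes first". SAP 5.6.2: "Adverse events with a starting date 30 or more days after the last dose date are not considered TEAEs". The observation window therefore follows treatment duration plus about 30 days.

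**Expected durations.** Protocol 10.2 and SAP 5.1 both assume median PFS of 4 v 7 months. The SAP otherwise describes a larger 2:1 trial with an exemestane option, but this assumption is common to both documents.

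**What already reflects exposure.** SAP 5.6.1 summarises cycles started and derives exposure: "Total Exposure (weeks) derived as (last dose date first dose date + 1"). SAP 5.6.2 also lists "Any TEAE by PT by cycle" and "Any TEAE by PT by NCI CTCAE Grade by cycle". No denominator is given for these two tables, and derived exposure does not enter any adverse event analysis.

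**The concern.** A percentage of treated patients estimates the chance of an event during however long each patient was watched. When one arm is expected to be watched longer because the drug works, that percentage mixes toxicity with efficacy. Two arms with the same monthly risk would then give different percentages. If seribantumab patients instead stopped early for toxicity, the distortion would run the other way and could hide harm.

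Describing the safety profile is a secondary objective (Protocol 2.2). Protocol 5.2.5.1 expects more low-grade diarrhea, rash and hypokalemia, among others, and says pulmonary embolism may be more frequent. The arm difference in these events is what a reader will look at.

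**Working it through.** **1. Inputs from the documents.** Median PFS 4 v 7 months, 16 months' accrual, 20 months in total, 1:1 (Protocol 10.2); 30-day window (SAP 3.6.1, 5.6.2).

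**2. The plan's own figure.** Protocol 10.2 claims "80% power to detect a hazard ratio (HR") of 0.57 or less with 58 events at one-sided 0.10. Schoenfeld's formula gives 58 events, and 58 events give 80.5% power. The 4 v 7 month assumption is therefore the one on which the trial is sized.

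**3. Assumptions not in the documents.** Time on treatment is exponential and follows PFS. The adverse event hazard L is constant and equal in both arms, shown from 0.5% to 20% per month. Accrual is uniform, so follow-up C at the cut-off is uniform on 4 to 20 months.

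**4. Without a cut-off.** Let mu = ln2/median, which is 0.1733 (control) and 0.0990 (seribantumab) per month, and w = 30/30.4375 = 0.986 months.

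Crude % = 1 - [mu/(mu + L)] x exp(-L x w)

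At L = 0.05:
- control: 1 - (0.1733/0.2233) x 0.9519 = 26.1%
- seribantumab: 1 - (0.0990/0.1490) x 0.9519 = 36.7%

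Mean time on treatment is 1/mu = 5.8 v 10.1 months.

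**5. With the 20-month cut-off.** The patient is observed to min(T + w, C), where T is time on treatment. For fixed C:

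Crude % = 1 - { exp(-L x w) x [mu/(mu + L)] x [1 - exp(-(mu + L)(C - w))] + exp(-mu(C - w)) x exp(-L x C) }

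This is averaged over C. Mean time on treatment falls to 4.8 v 6.7 months.

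| Monthly hazard, both arms | Control | Seribantumab | False excess (points) | False excess, no cut-off |
|---|---|---|---|---|
| 2% | 10.3% | 13.3% | 2.9 | 6.3 |
| 5% | 23.2% | 29.0% | 5.8 | 10.6 |
| 10% | 39.3% | 47.4% | 8.1 | 12.4 |
| 20% | 59.5% | 68.2% | 8.7 | 10.9 |

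**6. Where it is small or absent.**
- *Rare events.* At 0.5% per month the excess with cut-off is 0.8 points, or 0.008 x 40 = 0.3 of a patient per arm. Pulmonary embolism was seen in 3.1% and 4.3% of earlier seribantumab-plus-paclitaxel arms (Protocol 5.2.5.1).
- *Early events.* For an event that can start only in month 1, the on-treatment percentage is L/(L + mu) x [1 - exp(-(L + mu))]. At 10% per month this is 8.7% v 9.1%. With the 30-day window the gap essentially disappears.
- *Smaller PFS effect.* At the hazard ratio of 0.772 from the earlier exemestane trial, which was not selected on heregulin (Protocol 1.5.2.1), the excess is about 3 to 4 points at 5-20% per month. At a hazard ratio of 1 it is zero.

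**7. Does the remedy work?** Under identical hazards, first events per 100 patient-months at risk are 5.0 v 5.0, 10.0 v 10.0 and 20.0 v 20.0 at 5%, 10% and 20% per month. Onset within 8 weeks is 8.5% v 8.6% at 5% and 16.3% v 16.5% at 10%.

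**8. By-cycle tables.** At 5% per month, on-treatment risk per cycle among patients starting that cycle is 4.2% v 4.3%. If the whole arm is the denominator instead, the artefact returns: without a cut-off, cycle 8 shows 1.0% v 1.6%. The missing denominator therefore matters.

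**The case against.** - *The plan is not blind to timing.* This stands. The by-cycle table by CTCAE grade displays grades 3 and above, so a reader who inferred that severe events have no by-cycle display would be wrong. Cycles 1 and 2 span the first 8 weeks, and SAP 5.6.1 gives the number starting each cycle. The denominator may be set in the mock shells, which SAP 5.2 keeps outside the signed plan. What remains is that the plan states none, and that related events, SAEs, and events leading to discontinuation or death have no by-cycle table.
- *The excess is conditional.* This also stands. It needs a PFS benefit, time on treatment that follows PFS, and events that accrue. The documents give no onset pattern for diarrhea or rash.
- *It is within noise.* With 40 patients per arm at 10% per month, the standard error of the difference is sqrt(0.393 x 0.607/40 + 0.474 x 0.526/40) = 11 points, above the 8-point shift. That limits what one table can show, but a systematic shift is added to the noise and always runs the same way. In the SAP's 286-patient 2:1 design the standard error is about 6 points.
- *No test is planned.* Correct: these tables are descriptive. A description that depends on efficacy is still a poor one.
- *The DMC.* A reader might infer that the committee's safety view is distorted as well. Its displays are governed by a separate charter, so the documents do not support that.

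**Conclusion.** The point holds in a conditional form. Under the trial's own hypothesis, crude percentages for events that accrue over time would overstate seribantumab toxicity by about 6 to 9 points at monthly hazards of 5-20% and about 3 points at 2%. For rare events such as pulmonary embolism, and for events confined to the first month, the overstatement is under 1 point. These sizes rest on exponential time on treatment that follows PFS, a constant and equal hazard, uniform 16-month accrual and a 20-month cut-off.

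A reader might conclude that the plan will show excess toxicity regardless. The documents do not support that: with no PFS difference, and time on treatment following PFS, there is no artefact. The primary endpoint is untouched. This is an inexpensive improvement to a stated secondary objective that should be made before database lock.

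**What to change.** In Protocol 10.5.4 and SAP 5.6.2:

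1. Keep the crude tables.
2. Add first events per 100 patient-months at risk, with the arm difference and a confidence interval, for any TEAE, grade 3 or higher TEAEs, SAEs and the named risks (diarrhea, hypokalemia, rash, infusion reaction, pulmonary embolism or other venous thromboembolism). Time at risk runs from first dose to the earliest of first event, end of the TEAE window, or cut-off.
3. Add the percentage of patients with onset in the first 8 weeks for the same events.
4. State that the denominator of each by-cycle table is the number of patients starting that cycle.

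**Cost.** A few extra tables or columns from dates already collected. A rate per patient-month assumes a roughly constant hazard and can mislead for front-loaded events; the 8-week percentage beside it offsets this. For very rare events the interval will be wide and the rate will add little.
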